The study will be conducted in accordance with the ICH guidelines and in full compliance with ethical and deontological standards. Individuals participating in this study will be qualified by education, training and experience to perform their respective tasks.

The study population in this CEA is patients with an indication for elective, scheduled or early CL. The inclusion criteria are detailed below:

- Over 18 years of age.
- Autonomy, self-sufficiency and independence.
- Indication of CL programmed:
 - Symptomatic cholelithiasis: history of biliary colic, acute calculous cholecystitis, choledocholithiasis, acute ascending cholangitis of calculous origin or acute calculous pancreatitis.
 - Gallbladder polyps with indication for laparoscopic surgery.
 - Vesicular adenomyomatosis with indication for laparoscopic surgery.
- Indication for early LC (<72 hours of admission for acute calculous cholecystitis/acute calculous cholecystitis/complicated biliary colic).
- Indication of deferred emergency CL.
- Understanding information.
- Signing the informed consent form.

The exclusion criteria are detailed below:

- Under 18 years of age.
- Incapacity.
- Pregnancy or breastfeeding.
- Chronic kidney disease (Stage> IIIb).
- Adverse reactions or allergies prior to IV.
- Previous adverse reactions or allergies to VI excipients.
- Confirmed adverse reactions or allergies to iodinated contrast agents.
- Functional thyroid pathology (hyperthyroidism, thyroiditis, toxic multinodular goitre, functioning thyroid adenoma).
- Urgent non-deferrable/emergent gallbladder surgery.
- Initial surgery by laparotomy.
- Previous suspicion of gallbladder carcinoma.
- Inability to understand the information needed to participate in the study.
- Refusal of inclusion in the study protocol.

8. Aim and Purpose of the Trial

The objectives of this CE are detailed :

- **Main objective.** To analyse whether there are differences between different doses (single dose and weight-adjusted dose) and different VI administration intervals to achieve ideal visualisation of biliary structures during CF in LC.

- **Secondary objectives.**
 - 1. To analyse the influence of body mass index on FC outcomes during CL.
 - 2. To analyse the influence of the type of biliary pathology requiring surgery on the results of FC during LC.
 - 3. To analyse the influence of the type of surgery (elective/early/ delayed surgery) on the outcome of FC during LC.

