 - 4. To analyse the influence of previous inflammatory changes on the results of FC during LC.
 - 5. To analyse the influence of previous gallbladder or bile duct instrumentation on the results of FC during LC.
 - 6. To analyse the influence of different laparoscopic imaging systems on the results of FC during LC.
 - 7. To analyse the rate of intraoperative complications related to CF during LC.
 - 8. To analyse the rate of postoperative complications related to CF during LC.
 - 9. To analyse the impact of FC during LC on general surgeons and/or surgeons specialised in hepatobiliopancreatic pathology and their subjective assessment of the procedure.
 - 10. To assess the impact of a history of previous liver disease on fluorescein cholangiography.

[figure not shown]
9. Trial Design

For this JU, the following key variables to be assessed in the trial are determined. Primary variables:

- Identification of biliary structures prior to dissection of the hepatocystic triangle.
 - Identification of cystic duct (yes/no).
 - Identification of common bile duct (yes/no).
 - Identification of the junction of the cystic duct with the common bile duct (yes/no).
 - Identification of the junction of the cystic duct with the gall bladder (yes/no).
 - Identification of the common hepatic duct (yes/no).
 - Identification of anatomical variables (yes/no. Specify).
- Identification of biliary structures after dissection of the hepatocystic triangle.
 - Identification of cystic duct (yes/no).
 - Identification of common bile duct (yes/no).
 - Identification of the junction of the cystic duct with the common bile duct (yes/no).
 - Identification of the junction of the cystic duct with the gall bladder (yes/no).
 - Identification of the common hepatic duct (yes/no).
 - Identification of anatomical variables (yes/no. Specify).
- Degree of identification of biliary structures prior to dissection of the hepatocystic triangle (1=poor, 2=sufficient, 3=sufficient, 4=good, 5=excellent).

- Degree of identification of biliary structures after dissection of the hepatocystic triangle (1=poor, 2=sufficient, 3=sufficient, 4=good, 5=excellent).
- Degree to which fluorescence cholangiography was perceived as useful for surgery (0=not useful, 1=moderately useful, 2=very useful).

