20.12. Report to researchers

The sponsor will submit safety information that could impact the safety of the patients enrolled in the trial to the investigators as early as possible. In addition, the investigator will be informed throughout the study of any safety issues, including protocol modifications due to safety concerns.

21. Statistics

For the calculation of the sample size we estimated an average annual number of laparoscopic cholecystectomies of 300 cases. Assuming a minimum recruitment rate of 50% in the study, a duration of 12 months and possible losses of patients, we estimate a sample size of 200 patients.

Since the main objective is to analyse whether there are differences between the doses and administration times of the 4 treatment groups in which categorical variables will be measured, the effect of the chosen sample size ($n=200$) on the statistical contrasts in this type of variables is $w=0.25$ with a power.95 and a significance error of the null hypothesis $\alpha=0.05$.

The procedure used to account for missing, unused and erroneous data will be the "*Pairwise Delection*" method. The confidence intervals of the statistics will be 95% and the contrasts will be performed at a significance level of 5%. All analyses will be performed with the free software R (version 4.1.2+, R Core Team, Vienna, <https://www.R-project.org/>) and the RStudio interface (version 1.4.1103+).

The study will have no planned intermediate analyses as no partial analysis of results is envisaged. Once all data have been collected, verified and validated, a statistical analysis of the data will be performed according to the specifications described in the protocol. If this analysis leads to the conclusion that further analysis is necessary, this will be reported in the final analysis of results. All treated and evaluable subjects shall be analysed. Different statistical tools will be used depending on the nature of the variables collected in the study, accompanying the results with their corresponding graphs.

Lilliefors-Kolmogorov-Smirnov and Shapiro-Wilks tests shall be performed to study the normality of the distribution of quantitative variables, and to their distribution they shall be represented by the mean (standard deviation) or the median (median deviation) and may be accompanied by their corresponding confidence intervals. The relationship between such variables shall be measured with Pearson's or Spearman's correlation coefficients.

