The distributions of the categorical variables will be studied by means of frequencies and percentages. To represent and measure the dependence between them, contingency tables will be used with Pearson's Chi-square test, Fisher's exact test, McNemar's test

or Cochran's Q. A category comparison study could also be done using odds ratios between categories of clinical interest. To study the influence that some categorical variables might have on quantitative variables, ANOVA tests could be performed.

Finally, all the statistical information obtained on the relevance of each variable in the study could be used to apply classification tools to the individuals in the study (decision trees, logistic regression, ROC curves).

22. Direct Access to Source Data/Documents

The Promoter will enter into appropriate arrangements to appoint a monitor to oversee this study and to liaise regularly with the site, including arranging site visits. The investigator agrees to allow the monitor direct access to all relevant documents and to give his/her time and that of his/her staff to the monitor to discuss the results and any issues of concern.

23. Quality Control and Quality Assurance

In order to ensure the quality of the data, the promoter:

- Provide quality instruction and training to the research staff prior to the start of the study. Training topics include, but are not limited to: Good Clinical Practice (GCP) certificates, Adverse Event (AE) reporting, study details and procedures, study documentation, informed consent, and patient recruitment.

- Conduct regular monitoring in accordance with the International Conference on Harmonisation (ICH) for Good Clinical Practice (GCP). Data will be assessed for compliance with the protocol and for accuracy in relation to the source documents. Monitors will verify that the clinical trial is conducted, that data are generated, documented and reported in compliance with the protocol, good clinical practice and any applicable local regulatory requirements.

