In these secondary objectives, we tried to analyse predictors of the quality of the fluorescence technique. To this end, we have found numerous factors in the literature that could influence cholangiography. We want to show whether there are differences between the factors listed below and the different working groups.

a) To analyse the influence of body mass index on FC outcomes during CL.

In this section, we could recode the qualitative variable BMI into the different BMI subgroups defined by the World Health Organisation or use normal weight/overweight as the cut-off point.

Clasificación	IMC (Kg/m ²
Normal	18.5 - 24.9
Sobrepeso	25 - 29.9
Obesidad grado I	30 - 34.9
Obesidad grado II	35 - 39.9
Obesidad grado III	Más de 40

We could also analyse it as a quantitative variable and see if there is a correlation between them.

b) To analyse the influence of the type of biliary pathology requiring surgery and previous liver disease on the results of FC during LC.

Analyse whether there are differences between "Previous liver disease (NO/SI). In the SI group, break down the variables: fatty liver disease, hepatitis, liver cirrhosis". And the main variables shown.

c) To analyse the influence of the type of surgery (elective/early/ delayed surgery) on the results of FC during LC.

To analyse whether there are differences between the variables "type of surgery" and "indication for surgery".

d) To analyse the influence of previous gallbladder or bile duct instrumentation on the results of FC during LC.

To analyse whether there are differences between the variables "previous biliary explorations", "previous biliary prostheses" and "previous gallbladder drainage". Both separately and united in a single variable.

e) To analyse the influence of different laparoscopic imaging systems on the results of FC during LC.

To analyse whether there are differences between the variable "image system" and the main target variables.

f) To analyse the rate of intraoperative complications related to CF during LC.

To analyse intraoperative complication rates in the series.

g) To analyse the rate of postoperative complications related to CF during LC.

To analyse the postoperative complication rate for the series overall and for each type of Clavien-Dindo classification (consecutive variable).

Also to analyse separately the rate of bile duct injury and the characteristics of bile duct injuries (consecutive variables).

Analyse in-hospital and 30-day mortality rates.

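### SAP section 3 a)–e) asks for the influence of non-randomised factors without committing to any adjusted analysis, so a factor with no effect of its own may appear influential

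*SAP*

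**What the plan says.** SAP section 3 opens with "In these secondary objectives, we tried to analyse predictors of the quality of the fluorescence technique". Its items a) to e) are each titled as the influence of something on the fluorescence results. The operational text under them is uneven:

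- a) BMI may be recoded into classes or correlated as a continuous variable.
- b) Previous liver disease is set against the main variables. Type of biliary pathology is in the title but not in the instruction.
- c) Type of surgery and indication are named, but no outcome.
- d) Three instrumentation variables are named, singly and merged, but no outcome.
- e) "To analyse whether there are differences between the variable 'image system' and the main target variables".

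These items come from protocol section 8. Objective 6, for example, reads "To analyse the influence of different laparoscopic imaging systems on the results of FC during LC". Seven of the ten secondary objectives (1 to 6 and 10) ask about a factor of this kind. Objective 4, previous inflammatory changes, has no item in SAP section 3.

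On method, protocol section 21 says "contingency tables will be used with Pearson's Chi-square test, Fisher's exact test, McNemar's test" or Cochran's Q, with ANOVA possible for quantitative variables. The only multivariable option is that the information gathered "could be used to apply classification tools to the individuals in the study (decision trees, logistic regression, ROC curves"), with no outcome, covariates or purpose of adjustment given. The SAP's closing note repeats that sentence and asks for it to be explained.

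On eligibility, protocol sections 7 and 11.1 give "Indication for early LC (<72 hours of admission for acute calculous cholecystitis" or complicated biliary colic as the early-surgery route. Polyps and adenomyomatosis are listed only under scheduled surgery.

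**The concern.** Randomisation protects the comparison of G1 to G4. It does not protect comparisons between elective and early patients, or between patients imaged on different systems. When two such factors go together and one of them affects visualisation, a two-way table for the other shows a difference even if that other factor does nothing.

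The documents make both ingredients plausible for at least one pair. Eligibility links type of surgery to indication. Protocol section 7 says that inflammatory change could favour misidentification of the anatomy, and that visualisation rates differ with the patient, the pathological process, the technique and the instruments. Section 30 adds the surgeon as a source of variation. Protocol section 14 points to two hospitals, yet hospital is not among the variables listed in the SAP.

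At stake is what the trial reports for seven secondary objectives. A reader could be told that the timing of surgery or a make of camera influences fluorescence when the difference belongs to inflammation or to the hospital.

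**Working it through.** **1. The plan's own figure.** Protocol section 21 states that "the effect of the chosen sample size ($n=200$) on the statistical contrasts in this type of variables is $w=0.25$ with a power.95" at alpha 0.05. The noncentrality is λ = n·w² = 200 × 0.25² = 12.5. Power is 0.942 with 1 degree of freedom, which agrees with 0.95 to within a point. With 3 degrees of freedom (four groups by a yes/no outcome) it is 0.856, and 0.95 would need w = 0.293 or N = 275. The present point does not depend on this figure. From it I take only n = 200 and the 5% level.

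**2. Inputs.** The documents give no non-elective share (SAP section 1 says only that most cases, at least in the author's centre, were elective), no frequency of acute indication by type of surgery and no identification rates. All of the following are assumptions:

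- non-elective share: 10%, 20% or 30%;
- acute indication in elective and non-elective patients: 15% and 90% (strong link), 20% and 70% (weaker link), or 20% and 20% (no link);
- identification: 80% without acute indication; 80%, 70%, 60% or 50% with it;
- type of surgery has no effect once indication is fixed.

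**3. The spurious difference.** It equals (difference in acute indication) × (drop in identification). For the strong link and a drop from 80% to 60%:

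- elective: 0.15 × 0.60 + 0.85 × 0.80 = 0.77
- non-elective: 0.90 × 0.60 + 0.10 × 0.80 = 0.62
- difference: (0.90 − 0.15) × (0.80 − 0.60) = 0.15
- odds ratio: (0.62/0.38) / (0.77/0.23) = 0.49

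**4. How often it would be significant, by hand.** With 20% non-elective there are 40 and 160 patients, and the pooled rate is 0.2 × 0.62 + 0.8 × 0.77 = 0.74.

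- null SE = √[0.74 × 0.26 × (1/40 + 1/160)] = 0.0775
- actual SE = √[0.62 × 0.38/40 + 0.77 × 0.23/160] = 0.0836
- rejection ≈ Φ[(0.15 − 1.96 × 0.0775)/0.0836] = Φ(−0.02) = 49%

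**5. By simulation.** 8,000 trials of 200 patients per setting; percentage of trials in which the unadjusted chi-square rejects the null factor:

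| Link | Identification if acute | 10% non-elective | 20% | 30% |
|---|---|---|---|---|
| Strong | 70% | 13.3 | 18.8 | 22.0 |
| Strong | 60% | 32.2 | 49.3 | 57.7 |
| Strong | 50% | 56.1 | 77.8 | 86.5 |
| Weaker | 70% | 9.3 | 11.5 | 13.0 |
| Weaker | 60% | 18.1 | 27.3 | 31.6 |
| Weaker | 50% | 30.9 | 46.8 | 55.0 |

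With no link, or with no true effect of indication, the unadjusted test rejected in 4.6% to 5.4%. A Cochran-Mantel-Haenszel test stratified by indication rejected in 4.5% to 5.5% in every setting.

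**The case against.** The other side has a fair case. These are secondary, non-randomised analyses, and the SAP's own word is predictors, for which a marginal association is legitimate if it is labelled as one. One-factor testing against the main variables is explicit only in b) for liver disease and in e) for imaging system, and neither belongs to the pair linked by eligibility. Item c), read literally, cross-tabulates type of surgery with indication and tests no outcome. The protocol does allow logistic regression. Every rate above is assumed. A model with every SAP category would also be too large: about 23 parameters against roughly 52 non-identified patients (0.26 × 200 in the worked example), or 2.3 per parameter.

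Most of this stands, and it limits the point. A reader might infer that the eligibility rules tie several of these factors together and that a null factor will therefore be reported as influential. The documents do not support that. Eligibility links only type of surgery with indication, and only in part: scheduled surgery admits a history of acute cholecystitis, and deferred emergency surgery has no diagnosis attached. Links of drainage or ERCP with pathology, or of imaging system with hospital, are plausible but not shown. A false finding also needs a true effect of the linked factor.

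What the objection does not remove is that the items are titled as influence, that nothing commits the analyst to adjustment, and that the one sentence allowing it is optional, undefined and left as an open query in the SAP.

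**Conclusion.** The plan commits to no analysis that could separate linked non-randomised factors, so its influence objectives may credit one factor with another's effect. The documents establish the risk for type of surgery and indication. For the other factors it is only a possibility.

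The size depends on assumptions. In 200 patients, unadjusted rejection of a null factor was about 9% to 87% when a link and a true effect of the linked factor were both present. It was about 5% when either was absent or after stratification. The direction and the benefit of adjustment held throughout the grid; no single value in it should be read as a forecast.

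This should be corrected before the secondary results are reported. It does not touch the main objective.

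**What to change.** - Name a small set of key outcomes from the 16 listed in SAP section 2, and state the outcome in items c) and d).
- Keep the unadjusted tables and add one prespecified logistic or ordinal model per key outcome. Include randomised dose and time, hospital, BMI, type of surgery, acute or inflammatory indication or previous cholecystitis (collapsed), any previous instrumentation (yes/no), liver disease (yes/no) and imaging system. Report adjusted odds ratios with 95% CI.
- Limit the parameters to what the event count supports. With two hospitals and linear BMI, this list has 1 + 1 + 1 + 1 + 2 + 1 + 1 + 1 + 2 = 11. Against about 52 non-identified patients that is 4.7 per parameter, so the SAP should say in advance which terms are merged or dropped first.
- Where factors overlap too little to separate, show the cross-table, report them jointly and call the result an association. This applies to type-by-indication cells that are empty by design, and to imaging system by hospital if the cross-table shows it.
- Resolve the SAP's closing note accordingly.

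The cost is SAP wording, modest analysis and wider intervals. Most covariates are already collected, and the patient code identifies the centre (protocol section 13). A simulation of an 11-parameter model kept the test size at 5.4%, so the price is precision and sparse cells rather than validity. If the sponsor does not want the model, the minimum is to relabel a) to e) as descriptive associations.

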The investigational medicinal product is Verdye. Verdye (*Diagnostic Green* GMBH, Aschheim-Dornach, Germany) contains the active substance VI sodium as a powder for solution for injection. This product is approved by the US Food and Drug Administration (FDA), the European Medicines Agency (EMA) and the Spanish Agency for Medicines and Medical Devices (AEMPS) as of 30/8/2017. It is a medical device for hospital use and authorised diagnostic centres. VI is a water-soluble agent with a peak spectral absorption of 800 nm. Once administered intravenously, it has an affinity for plasma proteins (β -apolipoprotein B in 95% of cases), remaining constant in the intravascular space. The IV does not undergo any metabolism process in the body. The uptake of the drug from plasma is exclusively hepatic, with biliary excretion within 30 minutes to 2 hours after intravenous injection. The fluorescent characteristics of the product appear after stimulation with near-infrared light beams (700-900 nm). It is indicated for cardiac, circulatory and microcirculatory diagnostics, liver function diagnostics and ophthalmic angiography.

Risks from the administration of the medicinal product are rare. Severe allergic reactions have been reported in one in 10,000 patients, causing symptoms such as: constriction of the throat, pruritus, blotchy skin, urticaria, coronary artery spasm, facial oedema, shortness of breath, chest tightness or pain, tachycardia, low blood pressure, dyspnoea, heart failure or cardiac arrest, restlessness, nausea, sensation of heat, flushing. The possibility of severe allergic reaction is higher in patients with severe renal insufficiency.

The route of administration of the IV will be intravenous, as specified in its data sheet. The drug administration protocols will be divided according to the dosage and time interval until surgery, as detailed below:

- **Dosage.** 2 groups: fixed bolus dose of 2.5 mg and bolus dose adjusted for body weight (0.05 mg/kg total body weight).

- **Time of administration.** On admission (>3 hours prior to surgery) and immediately preoperatively (15-30 minutes prior to surgery).

There is no treatment period as it is considered a diagnostic method. This period shall include intraoperative time.

The investigator shall ensure that this study is conducted in accordance with the principles of the 1964 Declaration of Helsinki and its subsequent revisions, GCP as well as

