- 4- **Postoperative control visit.** This will take place 30 days after the surgical intervention through the General and Digestive System Surgery Outpatient Department.

There is no treatment period as it is considered a diagnostic method. This period shall include intraoperative time.

A computerised block randomisation will be performed through CDRe. Participants will be assigned to each of the 4 treatment groups by non-stratified 1:1:1:1 randomisation.

As it is an intervention without a control group, blinding will not be performed in the trial. The end-of-study criterion will be completion of the follow-up period at the end of the trial. 30 days from the last patient included in the study.

19. Effectiveness Assessment

The following efficacy parameters shall be used:

- Degree identification of biliary structures prior to dissection of the hepatocystic triangle (1=poor, 2=sufficient, 3=sufficient, 4=good, 5=excellent).
- Degree of identification of biliary structures after dissection of the hepatocystic triangle (1=poor, 2=sufficient, 3=sufficient, 4=good, 5=excellent).
- Degree to which FC was perceived as useful for surgery (0=not useful, 1=moderately useful, 2=very useful).
- Degree to which the fluorescence of the liver background (contrast between liver and ducts) was perceived as disturbed (0=absence of disturbance, 1=slightly disturbed, 2=disturbed visualisation, but cystic-choledochal junction was clearly visible before dissection, 3=disturbed visualisation and cystic-choledochal junction was only visible after dissection, 4=very disturbed: it was impossible to visualise the biliary structures correctly).

20. Security Assessment

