DOTIG CLINICAL TRIAL (NCT05419947) STATISTICAL ANALYSIS

Study promoter	Castilla y Institute of Health Sciences Studies Foundation (IECSCYL)- Institute of Biomedical Research of Salamanca (IBSAL)	
EUDRA CT number	2022-000904-36	
Promoter's Protocol Code	IBS-DOTIG-ECM-2202	
Title	Randomised clinical trial to evaluate the dose and time of administration of indocyanine green in near-infrared fluorescein cholangiography during laparoscopic cholecystectomy.	
Date	16/12/2022	

1. Working hypothesis. There are differences in the visualisation rates of extrahepatic biliary structures as a function of drug dose and time of administration.

To test the hypothesis, we created four intervention groups combining two doses (fixed dose of 2.5 mg and weight-adjusted dose ratio of 0.05 mg/kg body weight) and two administration times (15-30 minutes preoperatively and >3 hours preoperatively). The primary endpoints are dichotomous and polytomous qualitative variables.

Before analysing the main and secondary objectives, the groups (G1, G2, G3, G4) and their baseline characteristics should be compared in order to demonstrate that they are homogeneous and the randomisation has been correct. To do this, the following variables collected in the CRDe should be compared:

- Sex (male/female)
- Age (years)
- BMI (kg/m2)
- ASA classification (ASA I/II/III/IV/IV/V)
- Previous abdominal surgeries (NO/SI). In the YES group, break down the variables biliary/liver/pancreas/intestinal/other).
- Previous liver disease (NO/SI). In the SI group, break down the variables: fatty liver disease, hepatitis, liver cirrhosis.
- Previous biliary examinations (NO/SI). In the SI group, break down the ERCP/CTPH variables.
- Previous biliary prostheses (NO/YES)
- Previous acute cholecystitis (NO/SI).
- Previous acute cholangitis (NO/SI).

- Previous gallbladder drainage (NO/SI). In the SI group, break down the variables percutaneous cholecystostomy/endoscopic cholecystostomy.
- Indication for surgery (biliary colic/acute cholecystitis/choledocholithiasis/acute cholangitis/acute lithiasic pancreatitis/bladder polyps/bladder adenomyomatosis).
- Type of surgery (elective/early/deferred surgery). Probably in this variable we do not have a very similar N, because most of them, at least in our centre, were elective.
- Grade of cholecystitis (1/2/3). In case of early indication/delayed urgency.
- Imaging system (Olympus/Karl-Storz/Stryker)
- Type of optics (30 degrees/ 0 degrees).

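### SAP 3(a) leaves three BMI codings open with none primary and specifies no by-regimen analysis, although the gap between the two dose regimens depends on body weight

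*SAP*

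**What the plan says.** Protocol section 8 lists the influence of BMI on cholangiography results as secondary objective 1. SAP section 3(a) offers three ways to study it, all permissive. BMI could be recoded into WHO subgroups, for which a five-row table is given. The analyst could instead "or use normal weight/overweight as the cut-off point", which that table places at 25 kg/m². Or, in the SAP's words, "We could also analyse it as a quantitative variable and see if there is a correlation between them". None is named as the main analysis, and the item does not say which outcomes it applies to.

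Item (a) contains no dose-regimen term and no analysis by arm. The lead-in to SAP section 3 does mention the arms, but as worded it compares the listed factors with the groups. It does not ask whether a factor's effect differs between groups. Item (h), on perceived usefulness, does ask for results in each group separately.

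The dose factor itself depends on weight. SAP section 1 describes "two doses (fixed dose of 2.5 mg and weight-adjusted dose ratio of 0.05 mg/kg body weight", and Protocol section 7 defines the second regimen as a "bolus dose adjusted for body weight (0.05 mg/kg total body weight". Protocol section 18 adds: "Participants will be assigned to each of the 4 treatment groups by non-stratified 1:1:1:1 randomisation". Weight, height and BMI are all recorded as numbers (Protocol section 14).

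**The concern.** There are two linked problems.

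The first is the open choice of coding. SAP section 2 lists 16 main variables: 12 yes/no items and 4 graded scales. With three BMI codings, that allows up to 16 × 3 = 48 BMI analyses. Protocol section 21 says that "the contrasts will be performed at a significance level of 5"%. If a categorised coding is used, part of the information in BMI is also lost.

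The second is the link with dose. Under the weight-adjusted regimen, mg/kg is constant. Under the fixed regimen it falls as weight rises. A single BMI effect taken over all four arms therefore averages two situations in which body size means different things for exposure. If the effect of body size differs between them, the pooled result describes neither and may show nothing.

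At stake is how well objective 1 can be answered, and whether the trial describes how the regimen comparison varies with body size.

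**Working it through.** **Inputs.** Regimens of 2.5 mg and 0.05 mg/kg (Protocol sections 7 and 18; SAP section 1). Total of 200 patients (Protocol section 21: "possible losses of patients, we estimate a sample size of 200 patients"), about 50 per arm. Cut at 25 and class limits at 25, 30, 35 and 40 (SAP 3(a) table). The documents give no BMI distribution, identification rate or BMI effect, so these are assumed below.

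**The plan's own figure.** No power is given for the BMI objective. The only design figure is power 0.95 at w = 0.25, n = 200, α = 0.05 for the main categorical contrasts. The noncentrality is 200 × 0.25² = 12.5. Power is 0.942 with 1 degree of freedom and 0.856 with 3. The stated value is thus matched only by a 1-df test. It says nothing about BMI and is not used further.

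**Step 1: dose by weight.** Adjusted dose = 0.05 × weight; ratio = adjusted dose / 2.5; fixed dose per kg = 2.5 / weight.

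| Weight (kg) | Adjusted (mg) | Ratio to 2.5 mg | Fixed arm (mg/kg) |
|---|---|---|---|
| 50 | 2.5 | 1.0 | 0.050 |
| 70 | 3.5 | 1.4 | 0.036 |
| 90 | 4.5 | 1.8 | 0.028 |
| 100 | 5.0 | 2.0 | 0.025 |

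The regimens coincide only at 50 kg and diverge steadily above it. This follows from the documents' figures alone.

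**Step 2: information kept by categorising.** For a normal variable with a linear effect, a single cut keeps φ(z)² / [p(1 − p)], where z = (25 − mean)/SD and p is the share below 25.

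- Mean 28, SD 5: z = −0.6, φ = 0.333, p = 0.274. Then 0.111 / 0.199 = 0.56, so 200 patients act like about 112.
- Mean 26-29, SD 4-5: 0.44 (mean 29, SD 4) to 0.63 (mean 26, SD 5).
- Mean 25-30, SD 4-6: 0.35 to 0.64.

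Five classes keep 0.76 to 0.91 over that wider grid (0.87 at mean 28, SD 5). The top classes are thin: at mean 28, SD 5, about 14 of 200 patients fall in 35-39.9 and 2 of 200 at 40 or more.

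**Step 3: what pooling could do.** Logistic simulation with 200 patients, half on each regimen. BMI is normal (mean 28, SD 5), identification is about 70%, slopes are log-odds per SD of BMI, and there are 1,000 runs per scenario (simulation error about ±0.03). Entries are power at 5%.

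| Slope, fixed / adjusted | Pooled, continuous | Pooled, cut at 25 | Interaction, continuous | Interaction, cut at 25 |
|---|---|---|---|---|
| −0.5 / −0.5 | 0.89 | 0.64 | no interaction present | no interaction present |
| −0.7 / 0 | 0.56 | 0.31 | 0.57 | 0.34 |
| −1.0 / 0 | 0.80 | 0.51 | 0.84 | 0.55 |
| −0.5 / +0.5 | 0.05 | 0.05 | 0.89 | 0.65 |

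With equal slopes, pooling hides nothing and only the coding matters; classes, with 35 and over merged, give 0.71. If BMI acts only under the fixed dose (−0.7), the average pooled slope is −0.33, about half the true slope in those arms and wrong for the others. With opposite slopes the pooled test has no more power than its significance level.

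**The case against.** **The loss is conditional.** A reader might infer that the plan throws away a large part of the BMI data. The documents do not support that. Item (a) also permits BMI as a quantitative variable, and the five classes lose far less than the single cut. This stands. The quantitative option does not close the gap, however. Protocol section 21 gives Pearson and Spearman coefficients for relations between quantitative variables, while SAP section 1 calls the primary endpoints qualitative. A correlation would give at best a test of trend, with no effect estimate by regimen.

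**The cut-off is not free.** A reader might also infer that the cut can be picked after seeing the data. It cannot: the SAP's table fixes it at 25. What is open is the choice among codings.

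**The differing effect is not established.** It is tempting to say that the design contains a weight-by-regimen effect which the analysis hides. What the design contains is a dose difference that grows with weight. No passage says that visualisation responds to it, BMI is only a proxy for weight, and a pooled estimate across randomised arms is a legitimate average answer to objective 1. This stands, and limits the second problem to a possibility.

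**Regimen is not wholly ignored.** The lead-in to SAP section 3 mentions the groups, and Protocol section 21 allows logistic regression. But the lead-in sets out no effect-modification analysis. Logistic regression appears only as a possible classification tool, which the SAP's closing note leaves for discussion.

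**The power gain is uneven.** If BMI acts only under fixed dosing, the interaction test is hardly more powerful than the pooled test (0.57 against 0.56). The gain there is a correct description of each regimen, not power.

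**Conclusion.** The point holds in limited form. SAP 3(a) leaves three codings open, ranks none of them, and specifies no interaction or by-regimen analysis, although the dose difference between regimens varies with weight.

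The size depends on what is done. The single cut keeps about 44-63% of the information (35-64% under wider assumptions) and five classes about 76-91%. Continuous coding keeps all of it. These figures assume normal BMI and a linear effect, and the BMI means and SDs are not from the documents. The dose divergence is certain. That body size acts differently under each regimen, and that pooling would dilute or miss it, is a hypothesis; the simulated powers rest on assumed slopes.

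This is a secondary objective, and the primary randomised comparison is unaffected. The change is worth making because it is cheap and gives a better answer from data already collected.

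**What to change.** Rewrite SAP 3(a) so that one analysis is primary and its outcomes are named:

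- Fit a logistic model for the yes/no outcomes, or an ordinal model for the graded ones. Include continuous BMI (or weight, which drives the dose difference), regimen (fixed or weight-adjusted), timing, and a regimen-by-BMI (or weight) interaction. Choose BMI or weight in advance.
- Report the interaction as an estimate with a 95% CI, and give fitted results for each regimen at a few stated body sizes. Do not read a non-significant interaction as showing equal effects.
- Use WHO classes for description only.

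The cost is SAP wording and one model; Protocol section 14 already has weight, height and BMI recorded. No dose, visit or procedure changes. The downside is limited power for the interaction at 200 patients (0.57 for an assumed slope of −0.7 in the fixed arms and none in the adjusted arms), so its interval will be wide.
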